## SECTION 2: GENERAL INFORMATION

1. How many Human Research studies does the PI have open?

**8**

2. How many research staff will be involved in the Human Research?

**3**

3. What is the expected length of this project?

**18 months**

4. Retention of study materials before, during, and after completion of the project:

a. Where will original signed consent and PHI Authorization documents be stored (building name and room)? Location:

**Psychology room 312**

How long will consents be maintained after conclusion of the project?

6 years (UA standard)  6 years after child reaches 18  Other (explain):

5. Project funding - If the proposed study is or will be funded, complete below:

a. UAccess

i. Development Proposal #:

ii. Institutional Proposal #: 4206880

b. eDoc # (Required for For-profit sponsored research):

c. Total funding amount **OR** per subject amount: **\$15,000 from the Mind & Life Institute (Varela Award to [name])**

*Submit complete copy, cover-to-cover, of grant or award.*

6. Conflict of Interest (COI):

The Principal Investigator hereby affirms that ALL individuals who meet the definition of [investigator](#) for this project in the current *Policy on Investigator Conflict of Interest in Research* have completed the mandatory [Conflict of Interest training](#) and [Disclosure of Significant Financial Interests](#).

Yes - All individuals who meet the definition of "investigator" have completed COI training and disclosure.

No (explain):

7. Additional requirements:

Certain types of research require additional regulatory documentation. Please identify which of the following apply to your project. Complete the appropriate Appendix and submit as part of the submission materials.

Children (subjects under 18) - Appendix A

Drugs/Devices (A clinical investigation of a drug or device) - Appendix B

Multi-Site study (The UA IRB will review research activities for an investigator or research staff not affiliated with the UA who is 'engaged in the research' (e.g. consenting, collecting data, or analyzing identifiable information) - Appendix C

Pregnant Women/Neonates - Appendix D

Prisoners - Appendix E

Waivers of consent, waiver of a signature, or waiver or alteration of PHI - Appendix F

None apply to the proposed study

8. Location of Research **Check all that apply**

Banner – University Medicine Group:

- Phoenix Campus
- Tucson Campus
- South Campus

- Biological specimens
- Biological specimens
- Biological specimens

- Clinical Data
- Clinical Data
- Clinical Data

University of Arizona Cancer Center:

- North Campus
- Orange Grove Clinics
- Phoenix

- Biological specimens
- Biological specimens
- Biological specimens

- Clinical Data
- Clinical Data
- Clinical Data

Other: University of Arizona, Department of Psychology (Biological specimens)

**SECTION 3. PROJECT NARRATIVE**

**1) Background**

The transition from adolescence to adulthood, particularly for college students, is accompanied by several major life changes and challenges. For many individuals, this is a period when one moves away from home, begins interacting with different peer groups, and has greater financial and academic responsibilities. The emotional stress associated with these changes is correlated with less time devoted to sleep, increased alcohol intake, reduced academic performance, and increased rates of anxiety disorders and/or depression.

Your Enlightened Side (plus more) (YES+) is a life skills workshop with a strong emphasis on breathing practices for reducing stress and increasing well-being. Additional stress management tools including meditation, yoga, and interpersonal exercises that impart social emotional learning skills and stress reduction strategies complement the breathing techniques.

The central practice taught in YES+ is a unique rhythmical breathing technique called Sudarshan Kriya. It is taught along with two preparatory breathing practices: an advanced form of *Ujjayi* breathing (breathing against airway resistance) and *bhastrika* (forceful nasal breathing). Collectively, these three breathing practices are referred to as Sudarshan Kriya Yoga (SKY).

Prior literature has demonstrated significant improvements in psychological and physiological outcomes of SKY in adults, including decreases in subjective stress, clinical and subclinical depression and anxiety, posttraumatic stress symptoms, impulsivity, and tobacco use, as well as increases in calm, mental focus, emotion regulation, and overall well-being.

However, little is known about the effects of SKY specifically taught in the YES+ workshop format designed for college students. One randomized controlled trial has demonstrated attenuated levels of subjective stress and several hematological parameters, including lymphocytes and platelet count, during exam periods following SKY training. These findings have not yet been replicated, and the extent to which the effects of YES+ generalize to other health-related changes such as cardiovascular function remain unclear.

## 2) Purpose

Addressing the gap in the literature described above and to provide further preliminary data on the specific effects of YES+ on well-being and stress physiology, this study aims to evaluate measures of self-reported wellness across a variety of questionnaires, in addition to changes in heart rate variability and salivary cortisol levels with a stress induction task. To control for expectancy effects, overall time spent with the workshop, social contact, and exposure to cognitive stress management strategies that may influence the observed effects of YES+ not specific to the yogic breathing and deep social connectedness at the core of the YES+ targets, a comparison workshop with all of these potential supplementary contributors will be included, titled “Wisdom On Wellness” (WOW!).

## 3) Lay Summary (approximately 400 words)

While efficacy of Sudarshan Kriya Yoga (SKY) has been demonstrated in a number of prior studies, little is known about the effects of SKY taught as part of the Your Enlightened Side (YES+) workshop designed for college students. Thus, this study aims to assess the effects of YES+ on well-being, including sleep patterns, and physiological stress response.

## 4) Setting of the Human Research

Laboratory visits will be conducted in the Respiratory Physiology laboratory of [name], located in room 44 of the Ina Gittings Building (University of Arizona main campus). This room is set up for human subject experiments and is the site at which the [name] has conducted all previous research involving human participants.

Workshops will be conducted on the UofA campus in a room reserved through the Psychology Department or other campus reservation procedures.

## 5) Resources available to conduct the Human Research

[name] psychophysiology research laboratory (University of Arizona, Psychology Building, Room 409) has extensive experience with similar research protocols. Additional resources will be provided through collaborations with the Psychology Department’s Sleep Research Laboratory, which has more than 20 Actiwatches, a downloading station, and relevant software, as well as the Physiology Department’s Respiratory Physiology Laboratory, where the necessary resources are available for the laboratory visits. These resources include dedicated computers and software from Grass/Telefactor for electrocardiogram (ECG) data acquisition, processing, and analysis. In addition, the University of Arizona maintains full computer and data analytic processing components available to all university faculty on a fiber-optic network system, with automatic daily backup available on a secure server.

## 6) Study Population

**100 college students** (50% female) will be recruited into the current study. Persons expressing interest in the study will be screened along several health dimensions and invited to participate in the proposed research according to the following criteria:

- a) 18-35 years of age. This age range is recommended for the YES+ workshop to capture qualitative consistencies in the unique challenges that face college students and optimize social connectedness during the workshop.
- b) Current identification with student status, which may include undergraduate, graduate, continuing studies, or post-baccalaureate/pre-doctoral.
- c) No history of panic disorder, psychosis, or mania (with or without psychotic features), which may be risk factors for adverse effects of the yogic breathing intervention. These symptoms will be pre-screened via online questionnaire. The use of psychoactive medication will be monitored via sleep diary.
- d) No current substance dependence, assessed via online self-report pre-screening questionnaire.
- e) No current use of medications with known effects on sleep or stress physiology including antidepressants (SSRI, SNSI, NDRI, atypical, TCA, MAOI), antipsychotics, benzodiazepines, non-benzodiazepine receptor agonists, melatonin and melatonin receptor agonists, orexin/hypocretin receptor antagonists, barbiturates, mood stabilizers, anticonvulsants, anticholinergics, first generation antihistamines, and stimulants including NRI, antihypertensives, opioids, or systemic (non-topical) corticosteroids.

In addition, a total of **4 workshop instructors** are expected to enroll in this study to provide questionnaire information regarding expectancy of workshop benefit for participants. All instructors must have prior training with the specific workshop to be led.

## 7) Recruitment Methods and Consenting Process

### a. Recruitment Process:

Potential participants will be recruited primarily through the University of Arizona campus and broader Tucson communities. Potential subjects will be identified through targeted placement of study flyers in campus and community locations (e.g. bookstores, coffee shops, and community centers), and through placements of ads on websites (e.g. Facebook) and University listservs (University of Arizona 3D Memos, Lo Que Pasa, Psychology Department Graduate Student Listserv, etc.). Flyers and other advertisement may include the following language:

--

**Research participants wanted!**  
*Student Wellness Workshops*

With an aim to help students **reduce stress** and **enhance well-being**, the University of Arizona Psychophysiology Research Laboratory is investigating the effects of two innovative workshops on wellness and stress physiology.

Participation involves:

- Online questionnaires
- Three laboratory visits (approximately one hour each)
- Measurement of sleep patterns with a wrist-worn device
- Attendance at one workshop held across four consecutive days (Thurs & Fri evenings, Sat & Sun mid-day)

Compensation provided!

If you are a student 18-35 years of age, you may qualify! Invite friends to participate, too!

E-mail [[contact]](mailto:[contact]) for more info!

An Institutional Review Board responsible for human subjects research at The University of Arizona reviewed this research project and found it to be acceptable, according to applicable state and federal regulations and University policies designed to protect the rights and welfare of participants in research.

[figure not shown]
--

**b. Informed Consent:**

All interested individuals who are eligible for the study will undergo an in-person informed consent procedure prior to the first laboratory visit. Subjects, including workshop instructors, will be assigned identifying numbers and the association between the numbers and names will be destroyed upon completion of the study. No minors or individuals incompetent to provide informed consent will participate in the present study. They will be reminded that their participation in the study is entirely voluntarily, they may withdraw at any time, and they will be compensated for their time.

**8) Research procedures involved in the Human Research**

An overview of the study involvement is illustrated in Figure 1. Participation will include three laboratory visits at pre-workshop (T1), post-workshop (T2), and 1-2 month follow-up (T3) time points and four workshop sessions described below.

**Figure 1.** Overview of study timeline for each participant.

*Screening:* Interested participants will first be directed to an online pre-screening survey. The survey will begin with a prompt describing the study and requiring understanding via checkbox that the survey is for screening purposes. The survey will collect information such as name, e-mail address, date of birth, motivation for the study, student status, prior contemplative practice experience, ability to meet the time commitment, panic and bipolar symptoms, and potential affiliation with other

participants. If any of the exclusion criteria indicated above are met, the participant will be notified of ineligibility.

[figure not shown]
*Enrollment and randomization:* Eligible participants will be first grouped in clusters with any other participants with known affiliations stated in the online screener, in order to minimize possibility of learning about material of the other workshop, then assigned a workshop via random number generator.

*Laboratory Visits:* In-person laboratory visits will be conducted at the University of Arizona Respiratory Physiology Laboratory on the main UA campus. Workshops will be conducted in various buildings on the main UA campus depending on reservation availability.

Actigraphy, sleep diary, online questionnaires and practice logs measures will be completely remotely after the instruments are provided to participants during an in-laboratory visit.

In addition to actigraphy, sleep diary, online questionnaires, and home practice logs (for T2 and T3 time points) the following data will be collected during each laboratory visit: electrocardiography (ECG) with concurrent respiratory inductance plethysmography (RIP) and pulse oximetry recordings, as well as salivary cortisol at baseline, post-stress induction task, 30-min post-stress-induction-onset, and 45-min post. ECG, RIP belts, and pulse oximetry will be recorded continuously, in addition to the designated resting recording periods. An overview of the laboratory visit (identical across T1, T2 and T3) is provided in Figure 2.

*Workshop evaluations:* Both workshop participants and instructors will complete a brief questionnaire at two time points (end of Day 1 and end of Day 4) during the workshop to indicate expectation of workshop benefit.

**Figure 2.** Overview of each laboratory visit for data collection.

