***Intervention conditions:***

[figure not shown]
**YES+ workshop.** Your Enlightened Side, plus more (YES+) is an four-day, 15-hour eclectic life skills workshop with a strong emphasis on breathing techniques and social connectedness to enhance stress management, intervene in the potential negative behavioral cycles, and improve overall well-being. In addition to specific contemplative techniques such as yoga, mindfulness meditation, and compassion meditation that help cultivate inner peace, YES+ incorporates discussions and other activities to facilitate social connectedness, leadership, and community service.

During the workshop, participants will have ample time to learn and practice the Sudarshan Kriya Yoga (SKY) technique, as well as to ask questions. SKY has four sequential, form- and rhythm-specific breathing components interspersed with normal breathing while sitting in a relaxed position with eyes closed, followed by Yoga Nidra (tranquil state of rest) for 10-15 minutes in a supine position, yielding a total duration of approximately 30 minutes for the entire home practice. A longer version of SKY will be practiced as a group twice during the workshop. Following the workshop, participants will be instructed to practice SKY at home daily. A certified instructor with a minimum of 1,000 hours of SKY instruction training will lead each workshop.

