**WOW! workshop.** A comparison workshop titled “Wisdom On Wellness” (WOW!) will be implemented to control for potential expectancy effects, time commitment, group-based interactions, and wisdom/knowledge of YES+ that is anticipated to have beneficial effects on stress management and well-being, allowing for more rigorous evaluation of the contemplative practices and other activities unique to the YES+ workshop. The material used to guide interactions in WOW! will be similar to the material of YES+ and will be taught by a trained instructor with supervision by the Principal Investigator and Study Coordinator. This workshop differs from YES+ due to the increased focus on cognitive approaches to conceptualizing and managing stress (e.g. thoughts about the past and future versus present moment), and absence of physical or somatic activities. Using a focus group format, whereby the instructor primarily facilitates discussion, a variety of topics will be covered such as the nature of stress for humans, response to stressful events, time management, study skills, alcohol and drug use, personal values, career exploration, sleep habits, and nutrition.

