## 13) Subject compensation

The maximum total amount a participant may receive is \$100. Payment will be provided at two points across the study: \$60 upon completion of T2 and an additional \$40 upon completion of T3. This payment plan has been carefully devised to ensure adequate payment that is proportional to the challenge of maintaining commitment through the entire study, while not overly lucrative in order to minimize chance of possible coercion and/or substantial monetary motivation that would be detrimental to the workshop dynamics. To help ensure appropriate attendance at the workshops, which is critical to enable group cohesiveness as part of the workshop benefit for individual participants, payment will not be pro-rated for drop-outs prior to completion of T2.

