Effects of Two Psychosocial Wellness Workshops on Sleep, Stress Management and Wellbeing: Exploration of Psychophysiological Mechanisms

Brief title: Student Wellness Workshop study (SWW)

NTC number: not yet assigned

Date of document: 12/15/2017

Statistical analysis will be conducted in IBM SPSS 24.0 using Linear Mixed Models and selective post-hoc comparisons focusing on within-group change for YESplus and WOW at post and follow-up compared to pre-workshop. For each model, results will be reported for main effects of Visit (pre, post, follow-up) and Group (YESplus, WOW), as well as Visit x Group interaction. However, due to limited statistical power of this sample to detect interactions, analysis will focus on within-group change from pre- to post-workshop, as well as pre to follow-up, and corresponding within-group effect size. Thus, to balance type I and type II error with these within-group comparisons, a Bonferroni correction will be applied by multiplying uncorrected p values by 4 (the number of post-hoc comparisons per model), allowing alpha to remain at .05 for significance. Effect size estimates will be calculated with Cohen's d.

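### Both workshops are delivered in groups and participants are assigned by affiliation cluster, but the SAP names no term for workshop run or cluster, so the .05 level is not assured if change is correlated within runs

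*Protocol*

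**What the plan says.** **Assignment.** Protocol Section 3, item 8 (Enrollment and randomization): "Eligible participants will be first grouped in clusters with any other participants with known affiliations stated in the online screener". A random number generator then assigns the workshop. The stated reason is to limit contamination between arms.

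**Delivery.** Under Intervention conditions, for YES+: "A longer version of SKY will be practiced as a group twice during the workshop". For WOW!: "Using a focus group format, whereby the instructor primarily facilitates discussion". Item 13 (Subject compensation) justifies the payment rule by attendance, which it calls "critical to enable group cohesiveness as part of the workshop benefit for individual participants".

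**Number of runs.** Not stated. Item 8 mentions "four workshop sessions described below", but these are the four days that each participant attends, not four separate deliveries. The YES+ text says "A certified instructor with a minimum of 1,000 hours of SKY instruction training will lead each workshop", and item 6 (Study Population) expects four instructors in total. Both hint at more than one run, but neither settles it.

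**Analysis.** The SAP's single paragraph is the only analysis text. It specifies linear mixed models, for which "results will be reported for main effects of Visit (pre, post, follow-up) and Group (YESplus, WOW), as well as Visit x Group interaction". It puts the emphasis on within-group change from pre to post and pre to follow-up, and controls error by "multiplying uncorrected p values by 4 (the number of post-hoc comparisons per model), allowing alpha to remain at .05 for significance". It does not describe the random structure. Neither document names a random effect, variance correction or sensitivity analysis for run, instructor or affiliation cluster.

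**The concern.** People who go through the same four-day workshop share an instructor, a room, a date and each other. The Protocol expects the group itself to contribute to the benefit, so correlated change within a run is plausible on its own reasoning. If change is correlated, 50 people in a few runs carry less information about the workshop than 50 independent people. A model with only the named terms would then give standard errors that are too small.

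Two features of the plan do not protect against this. The Bonferroni step corrects for the number of comparisons, not for dependence between participants. A participant random intercept cancels from a change score, whereas a run-by-visit effect does not.

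At stake are the within-group p-values, which are the SAP's declared focus, and the between-group tests that it also reports. Confidence intervals would be too narrow in the same way.

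**Working it through.** **Inputs from the documents.** 100 students (Protocol item 6). Two groups, three visits, four within-group comparisons, and p-values multiplied by 4 and judged at .05 (SAP).

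**Assumptions, not in the documents.** 50 per arm; equal runs of 10 (five per arm) or 25 (two per arm); ICC of change 0 to 0.10; correlation 0.5 between the T1–T2 and T1–T3 changes, at run and at person level; no dropout.

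**Step 1: the plan's own figure.** Multiplying p by 4 is a per-comparison threshold of .05/4 = .0125, and 4 × .0125 = .05. The figure is reproduced. With independent participants, simulated family-wise error is 4.7–4.8%.

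**Step 2: design effect.** With m people per run, the variance of a mean change is multiplied by DE = 1 + (m − 1) × ICC. At ICC 0.02 / 0.05 / 0.10:
- m = 10: 1.18 / 1.45 / 1.90
- m = 25: 1.48 / 2.20 / 3.40

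**Step 3: actual error if run is ignored.**
- One comparison or one-degree-of-freedom contrast: 2 × (1 − Φ(z/√DE)), with z = 2.498 for .0125 and z = 1.960 for .05. Example, m = 10 and ICC 0.05: 2.498/√1.45 = 2.074, giving .038 instead of .0125.
- Visit × Group test: three visits and two groups give 2 numerator degrees of freedom. The large-sample level is exp(−5.991/(2 × DE)), provided that run effects on the two changes have the same correlation as the individual changes. Example, DE 1.45: exp(−2.066) = .127.
- Family-wise error of the four within-group tests: simulation of 40,000 trials with paired t tests and the fourfold correction.

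| Run size | ICC of change | Four within-group tests, family-wise (nominal 5%) | One between-group change contrast (nominal 5%) | Visit × Group, 2 df (nominal 5%) |
|---|---|---|---|---|
| 10 | 0 | 4.8% | 5.0% | 5.0% |
| 10 | 0.02 | 7.7% | 7.1% | 7.9% |
| 10 | 0.05 | 13.2% | 10.4% | 12.7% |
| 10 | 0.10 | 23.2% | 15.5% | 20.7% |
| 25 | 0 | 4.7% | 5.0% | 5.0% |
| 25 | 0.02 | 13.8% | 10.7% | 13.2% |
| 25 | 0.05 | 29.5% | 18.6% | 25.6% |
| 25 | 0.10 | 50.9% | 28.8% | 41.4% |

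**Step 4: affiliation clusters alone.** Suppose every participant were in a pair or a trio. DE at ICC 0.02 / 0.05 / 0.10 is 1.02 / 1.05 / 1.10 for pairs and 1.04 / 1.10 / 1.20 for trios. A nominal .05 test becomes 5.2 / 5.6 / 6.2% and 5.5 / 6.2 / 7.4%.

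**Step 5: price of accounting for run.** Detectable within-group change at 80% power, two-sided .0125, noncentral t with SE = √(DE/50) in SD of change:
- Run ignored (49 df): 0.49 SD.
- Five runs of 10 per arm, run variance pooled over arms (8 df, critical t 3.21): 0.59 / 0.64 / 0.71 / 0.81 SD at ICC 0 / 0.02 / 0.05 / 0.10.
- Same, not pooled (4 df, critical t 4.31): 0.78 / 0.85 / 0.94 / 1.08 SD.
- Two runs of 25 per arm, pooled (2 df, critical t 8.86): 1.95 / 2.38 / 2.96 SD at ICC 0.02 / 0.05 / 0.10.

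In simulation of 20,000 trials, tests on the means of five runs per arm kept family-wise error at 4.4–4.8% over ICC 0 to 0.10.

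**The case against.** The strongest reply is that this is an omission, not a demonstrated error. A linear mixed model can hold a run or cluster effect, and the SAP describes no random structure at all, not even for participant. That stands. A reader might infer that clustering was or will be ignored, or that the reported results are invalid. The documents show only that no such term is named.

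Second, the size is assumed throughout. Run effects that are constant over visits cancel from within-person change, so ordinary similarity within groups does no harm, and at ICC 0 the .05 level holds. That also stands. The 51% figure needs runs of 25 with an ICC of 0.10, and nothing in the documents favours it.

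Third, cluster assignment might look like the main fault. It is not: Step 4 shows that small affiliation clusters move the level very little. Workshop run drives the larger figures.

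Fourth, the Protocol's Purpose calls the data preliminary, the SAP's title speaks of exploration, and within-group effect sizes are part of its focus. This lowers the weight of the point. It does not remove it, because the SAP still judges significance at .05, and the Purpose aims at effects of YES+ rather than of particular deliveries of it.

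Fifth, with few runs the correction costs so much power that it may be unusable. Step 5 bears this out for two runs per arm. With one run per arm, run and arm cannot be separated by any model. The fix allows for both.

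**Conclusion.** The point holds in conditional form. The design assigns by affiliation cluster and delivers in groups, and the analysis names neither unit. If change is positively correlated within runs, run is left out, and the result is read as an effect of the workshop in general, then within-group and between-group standard errors are too small and the stated .05 level is not met. The fourfold correction does not change that. Point estimates and Cohen's d are not biased; p-values and intervals are affected.

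The size cannot be fixed from the documents. Under the assumptions in the working, family-wise error of the within-group tests runs from about 5% (ICC 0) to 23% with runs of 10, or to 51% with runs of 25. These figures show sensitivity and are not estimates for this trial. The point should be fixed, but it does not invalidate the study.

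**What to change.** 1. Keep workshop-run and affiliation-cluster IDs in the de-identified analysis file, and report the number and size of runs and clusters per arm. This is easiest before the link between names and numbers is destroyed at study completion (Protocol item 7b). The retained consent forms and intake dates (item 12b) may allow later recovery.
2. Add affiliation cluster, the unit of assignment, as a random effect on change where it can be estimated, or use a small-sample cluster-robust variance.
3. With several runs per arm, account for run on the change scale: a run-by-visit random effect or an analysis of run means, with degrees of freedom based on the number of runs. Do this at least as a prespecified sensitivity analysis beside the planned model, and say in advance whether run variance is pooled over arms.
4. With one or very few runs per arm, keep the planned model, limit conclusions to the workshops delivered, and emphasise estimates with intervals over p-values.

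**Cost.** Two ID columns, a few sentences in the SAP, and wider intervals. With five runs of 10 per arm and pooled run variance, detectable within-group change rises from 0.49 SD to about 0.59–0.81 SD over ICC 0 to 0.10. Part of that loss is paid even if the ICC is 0, which is a reason to allow the run-adjusted analysis to stand as a sensitivity analysis.
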